4.6.5 Power curves for secondary hypothesis tests about PE in each mAb group

Figure 4-4 shows unconditional power to reject the null hypothesis H0: $PE10 \le 0\%$ versus the alternative hypothesis H1: PE10 > 0% (or, equivalently, the null hypothesis H0: $PE30 \le 0\%$ versus the alternative hypothesis H1: PE30 > 0%), where PE10 and PE30 measure prevention efficacy in each mAb group separately.

[figure not shown]

Figure 4-4 Unconditional power to reject H0: $PE10 \le 0\%$ in favor of H1: PE10 > 0% (or H0: $PE30 \le 0\%$ in favor of H1: PE30 > 0%) based on primary assumptions about HIV-1 incidence rate and dropout rate (1-sided 0.025-level tests). Power curves are also shown for lower than expected HIV-1 incidence rate and a higher than expected dropout rate.

4.6.6 Rationale for the HIV-1 incidence assumptions

The assumption of 3% annual HIV-1 incidence in the control group accommodates background PrEP use by assuming incidence is decreased by two parameters: (1) the fraction of person-years at-risk during which PrEP is used; and (2) the level of efficacy of PrEP during PrEP use. Figure 4-5 shows the annual HIV-1 incidence in the control group as a function of these two factors, for a scenario where the annual HIV-1 incidence is 4% in the absence of any PrEP use. Based on HVTN 505 data (US participants only) through September 30, 2014, the annual HIV-1 incidence in the control group was 2.0% (95% CI 1.5%—2.7%) and in the vaccine and control groups pooled was 2.1% (95% CI 1.5%— 2.8%). From HVTN 505, based upon case report form (CRF) collection of PEP/PrEP med usage and responses to questions regarding usage posed on the 'anonymous' (to the site) ACASI questionnaire through June 1, 2014, 5% of participants reported ever using PrEP. In HVTN 505 the amount of person-years at risk during periods of PrEP use was likely well below 5%, and, therefore, the 2.1% annual incidence is a reasonable assumption for the baseline rate without PrEP. In particular, assuming 1.6% annual control incidence in the US and Switzerland (which is expected if 27% of person-years at risk are during PrEP use and PrEP efficacy is 90% during use) and assuming 5% annual control incidence in South American participants [7], (with 5% of person-years at risk during PrEP use and 90% PrEP efficacy during use), 44% of participants enrolled at South American sites would yield the assumed 3% annual control incidence rate.

[figure not shown]

Figure 4-5 Annual HIV-1 incidence in the control group assuming 4% annual HIV-1 incidence in the hypothetical scenario of no PrEP use, under different levels of PrEP use and levels of PrEP efficacy

Higher than expected use of PrEP would be reflected in lower than expected annual incidence rates, as shown in Figure 4-5. As shown in Figure 4-2, the trial would still provide enough statistical information to be powered to detect highly relevant prevention efficacy effect sizes if annual incidence rates are lower than we have estimated here due to higher than expected use of PrEP.

4.7 Power for the secondary analysis comparing HIV-1 incidence between the 10 mg/kg mAb group versus the 30 mg/kg mAb group

Table 4-4 reports power calculations for comparing HIV-1 incidence between the 10 mg/kg and 30 mg/kg mAb groups. The calculations assume the scenarios for true values of PE10 and PE30 indicated in the first two columns of the table. The results show that the study is well-powered to detect large differences, for example, with about 87% power to discriminate 30% vs. 80% PE and 40% vs. 85% PE, but may miss moderate differences (e.g., 34% power to discriminate 30% vs. 60% PE). In contrast, the study has high power to correctly select the best mAb dose group given moderate efficacy differences. Specifically, if the true PE30 is moderately greater than the true PE10, then there is high probability that the estimated PE30 would be greater than the estimated PE10, such that the 30 mg/kg mAb dose group would be selected.

		Power to Rank-and-Select	Power to Detect PE10
PE10	PE30	Best mAb Dose Group ^s	Different from PE30 [#]
20%	60%	88.3	58.3
30%	60%	86.7	39.5
40%	60%	81.7	21.6
20%	70%	97.2	83.7
30%	70%	96.8	69.4
30%	80%	99.8	91.5
40%	85%	>99.9	90.8
50%	85%	99.7	77.0

Table 4-4 Statistical power for comparing the 10 versus 30 mg/kg mAb groups: Power to correctly rank-and-select the best mAb group and power to detect superiority of the 30 mg/kg mAb group over the 10 mg/kg mAb group in a head-to-head comparison

⁵ Probability that the mAb dose group that is truly better (the 30 mg/kg dose group in the scenarios considered in the table) is correctly selected based on the point estimate for PE30 exceeding that for PE10. Specifically, correct selection entails that the estimated PE30 is greater than the estimated PE10 and PE30 is significantly > 0% (1-sided α = 0.025)

[#] Cumulative hazard-based 2-sided Wald tests comparing HIV-1 incidence between the 10 mg/kg and 30 mg/kg mAb groups. Rejection of the null hypothesis requires that PE30 is significantly > 0% (1-sided α = 0.025)

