4.9.3 Monitoring for futility to assess PE

The objective of monitoring the trial for futility to assess PE is to monitor progress toward the minimum needed target number of treatment arm-pooled HIV-1 primary endpoint infections by the Week 80 visit in the MITT cohort. Two targets are monitored for:

- 1. the total number of HIV-1 infections needed to achieve the planned 90% power to detect PE = 60%, and
- 2. the total number of HIV-1 infections needed to achieve 65% power to detect PE = 60%,

each using a 1-sided 0.025-level Wald test of H0: $PE \le 0\%$ against H1: PE > 0%, assuming proportional hazards of HIV-1 infection in the pooled VRC01 and control groups. The target numbers in (1) and (2) are 56 and 29, respectively (calculated by solving equation (1) in Schoenfeld [122]. The rationale for considering the two targets is as follows: (i) if the trial cannot achieve the planned 90% power to detect PE = 60%, considerations about enrollment modification or expansion are warranted, and (ii) if the trial cannot achieve even 65% power to detect PE = 60%, considerations about completing the trial early for futility to assess PE are warranted.

Two versions of the futility monitoring report will be generated. A report provided to the DSMB will be included in 6-monthly closed DSMB reports, starting in April 2018, and will report:

- a. the estimated distribution of the total (i.e., treatment arm-pooled) number of HIV-1 infections, with corresponding power to reject H0: $PE \le 0\%$ using a 1-sided 0.025-level Wald test under the alternative hypothesis PE = 60% throughout the trial,
- b. the estimated probability that the total number of HIV-1 infections is \geq 56 (target 1) with 95% credible intervals,
- c. the estimated probability that the total number of HIV-1 infections is ≥ 29 (target 2) with 95% credible intervals,
- d. the estimated distribution of the number of HIV-1 infections in each of the three treatment arms.

The distributions in (a) and (d) will also be summarized by the mean number of HIV-1 infections with a Wald 95% confidence interval. The estimation procedure for (a)–(d) will be conducted under each of the following two scenarios:

- the treatment arm-pooled infection rate in (a)–(c) and the three treatment armspecific infection rates in (d) used for generating future data are based on a Bayesian model and the prior assumption that PE = 60% (the design alternative), and

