- the treatment arm-pooled infection rate in (a)–(c) and the three treatment armspecific infection rates in (d) used for generating future data are based on a Bayesian model and the prior assumption that PE = 0% (the null hypothesis).

The reason for conducting the estimation procedure twice is that the purpose of the results for the 56 endpoint target (b) is to trigger considerations for trial modifications, whereas the purpose of the results for (c) is to trigger considerations for early trial completion due to futility, where it is desired to reach the guideline (b) more easily/readily than the guideline (c). Accordingly, the results for (b) are interpreted focusing on the prior of PE = 60%, which makes it more likely to reach a guideline than the prior of PE = 0%, and the results for the 29 endpoint target (c) are interpreted focusing on the prior of PE = 0%, which makes it less likely to reach a guideline than the prior of PE = 60%.

Furthermore, a treatment-blinded report will be generated for distribution to the OC after each DSMB meeting takes place and will report estimates listed in (a)–(c) above calculated based only on treatment-blinded data. The reported results pertaining to estimates (a)–(c) will be identical to those in the DSMB report.

While it is the primary responsibility of the OC to make decisions regarding trial operations and modifications based on the monitoring of treatment-blinded primary endpoints, given the resource issues involved, DSMB review is also needed because issues of scientific integrity are also involved. More specifically, the DSMB can evaluate the progress toward primary endpoint targets in the context of the treatment-unblinded data, and based on this review may recommend to the OC to complete the trial early due to reaching a guideline for futility to assess PE (specified below).

The monitoring for futility to assess PE includes the following guidelines for trial modifications:

- [Guideline for enrollment modifications] If, in the PE = 60% scenario for the prior distribution, the estimated probability of reaching 56 total infections is less than 25%, the OC may consider enrollment modifications with the intention to be able to conduct the primary PE analysis with adequate power.

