- [Guideline for futility] If, in the PE = 0% scenario for the prior distribution, the estimated probability of reaching 29 total infections is less than 25%, the DSMB may recommend completing the trial early based on the inability to conduct the primary PE analysis with adequate power. However, since this is a proof-of-concept trial, a high bar is desired for completing the trial early for futility, and therefore if this event occurs yet the non-efficacy monitoring has not started or the non-efficacy boundary has not been reached, then this guideline for futility also requires that the estimated PE for the pooled VRC01 vs. control arm is < 30% and the estimated PE for the VRC01 30 mg/kg vs. control arm is < 30%.

If enrollment is incomplete at the time of an interim futility analysis, then the outlined estimation procedures will use the average observed enrollment rate in approximately the

last 6 months for generating future enrollment data. In addition, a Bayesian approach will be used for generating future HIV-1 incidence data, conditional on observed data to-date. More specifically, the estimates in (a)–(c) will condition on the observed to-date treatment arm-pooled HIV-1 incidence rate, whereas the estimates in (d) will condition on the observed to-date (three) treatment arm-specific HIV-1 incidence rates. All estimates in (a)–(d) will also use the observed to-date treatment arm-pooled dropout rate for generating future dropout data.

If, at any time, these guidelines for futility to assess PE are met and yet it appears that value exists in continuing the trial, the statisticians will provide the DSMB and the OC with additional information, as appropriate, for use in their consideration of whether to recommend early trial completion.

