## 6 Interactions of Study Statisticians with the Data and Safety Monitoring Board

At each 6-monthly Data and Safety Monitoring Board (DSMB) meeting, the study statisticians will present Open and Closed Reports separately for each AMP trial; all tables and figures included in the Closed Report are specified in Appendix A with statistical analyses of safety further described in Section 7. For a subset of tables and figures in the Closed report, the Open Report includes tables and figures with the same information except with trial information presented pooled across the three treatment groups to preserve blinding to treatment assignment. In addition, the following trial monitoring reports will be presented at each DSMB meeting, separately for each AMP trial:

- feasibility monitoring report per Section 9.1 starting after approximately and not fewer than 120 enrolled participants have expected follow-up through to the end of the Week 32 visit;
- monitoring report of prevention efficacy for potential harm, non-efficacy, and high efficacy per Section 9.2, where
  - potential harm monitoring is commenced at the 20th pooled primary efficacy endpoint and is continually performed with each additional endpoint until the time non-efficacy/high efficacy monitoring is triggered,
  - non-efficacy monitoring is commenced at at least 45 but no more than 67 pooled primary efficacy endpoints, and
  - high efficacy monitoring is commenced at the same time as non-efficacy monitoring;
- monitoring report for the use of Truvada as pre-exposure prophylaxis per Section 9.3;
- monitoring report for futility to assess prevention efficacy per Section 9.4 starting after at least 12 months after the first participant is enrolled; and
- monitoring report for performance standards of quality of trial conduct per Section 9.5.

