## 9.4 Monitoring for Futility to Assess Prevention Efficacy

The objective of monitoring the trial for futility to assess PE is to monitor progress toward the minimal needed target number of treatment arm-pooled HIV-1 primary endpoint infections by the Week 80 visit in the MITT cohort. Two targets are monitored for:

1. the total number of HIV-1 infections needed to achieve the planned 90% power to detect  $PE = 60\%$ , and
2. the total number of HIV-1 infections needed to achieve 50% power to detect  $PE = 60\%$ ,

each using a 1-sided 0.025-level Wald test of  $H_0 : PE \leq 0\%$  against  $H_1 : PE > 0\%$ , assuming proportional hazards of HIV-1 infection in the pooled VRC01 and control groups. The target numbers in 1. and 2. are 57 and 21, respectively (calculated by solving equation (1) in Schoenfeld (1983)). The rationale for considering the two targets is as follows: (i) if the trial cannot achieve the planned 90% power to detect  $PE = 60\%$ , considerations about enrollment modification or expansion are warranted, and (ii) if the trial cannot achieve even 50% power to detect  $PE = 60\%$ , considerations about completing the trial early for futility to assess PE are warranted.

Two versions of the futility monitoring report will be generated. A report provided to the DSMB will be included in 6-monthly closed DSMB reports, starting in November 2017 for HVTN 703/HPTN 081 and in April 2018 for HVTN 704/HPTN 085, and will report:

- (a) the estimated distribution of the total (i.e., treatment arm-pooled) number of HIV-1 infections, with corresponding power to reject  $H_0 : PE \leq 0\%$  using a 1-sided 0.025-level Wald test under the alternative hypothesis  $PE = 60\%$  throughout the trial,
- (b) the estimated probability that the total number of HIV-1 infections is  $\geq 57$  (target 1) with 95% credible intervals,
- (c) the estimated probability that the total number of HIV-1 infections is  $\geq 21$  (target 2) with 95% credible intervals,
- (d) the estimated distribution of the number of HIV-1 infections in each of the three treatment arms.

The distributions in (a) and (d) will also be summarized by the mean number of HIV-1 infections with a Wald 95% confidence interval. The estimation procedures for (a)–(d) will be conducted under each of the following three scenarios:

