- (i) the treatment arm-pooled infection rate in (a)–(c) and the three treatment arm-specific infection rates in (d) used for generating future data are based on a Bayesian model and the prior assumption that  $PE = 60\%$  (the design alternative),
- (ii) the treatment arm-pooled infection rate in (a)–(c) and the three treatment arm-specific infection rates in (d) used for generating future data are based on a Bayesian model and the prior assumption that  $PE = 0\%$  (the null hypothesis), and
- (iii) the treatment arm-pooled infection rate in (a)–(c) used for generating future data is based on a Bayesian model and the prior assumption that the infection rate equals the observed to-date infection rate.

The reason for conducting the estimation procedure under (i)–(iii) is that the purpose of the results for the 57 endpoint target (b) is to trigger considerations about enrollment modifications, whereas the purpose of the results for the 21 endpoint target (c) is to trigger considerations about early trial completion due to futility, where it is desired to reach a guideline based on (b) more easily/readily than a guideline based on (c). Accordingly, the results for (b) are interpreted focusing on the prior of  $PE = 60\%$  (i.e., scenario (i)), which makes it more likely to reach a guideline than the prior of  $PE = 0\%$ , and the results for (c) are interpreted focusing on the prior of  $PE = 0\%$  (i.e., scenario (ii)), which makes it less likely to reach a guideline than the prior of  $PE = 60\%$ . Results for (b) and (c) based on carrying forward the observed to-date infection rate in scenario (iii) provide additional guidance to the DSMB regarding considerations about enrollment modification or early trial completion.

Furthermore, a treatment-blinded report will be generated for distribution to the Leadership Group before each DSMB meeting takes place and will report estimates listed in (a)–(c) above calculated based only on treatment-blinded data in scenarios (i)–(iii). The reported results pertaining to estimates (a)–(c) under scenarios (i)–(iii) will be identical to those in the DSMB report.

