While it is the primary responsibility of the Leadership Group to make decisions regarding trial operations and modifications based on the monitoring of treatment-blinded primary endpoints, given the resource issues involved, DSMB review is also needed because issues of scientific integrity are also involved. More specifically, the DSMB can evaluate the progress toward primary endpoint targets in the context of the treatment-unblinded data, and based on this review may recommend to the Leadership Group to complete the trial early due to reaching a guideline for futility to assess PE (specified below).

The monitoring for futility to assess PE includes the following guidelines for trial modifications:

- **Guideline for enrollment modifications.** If, in the  $PE = 60\%$  scenario for the prior distribution in (i), the estimated probability of reaching at least 57 total infections is less than 25%, the Leadership Group may consider enrollment modifications with the intention to be able to conduct the primary PE analysis with adequate power.

- **Guideline for futility.** If, in the PE = 0% scenario for the prior distribution in (ii), the estimated probability of reaching at least 21 total infections is less than 25%, the DSMB may recommend completing the trial early based on the inability to conduct the primary PE analysis with adequate power. However, since this is a proof-of-concept trial, a high bar is desired for completing the trial early for futility, and therefore if this event occurs yet the non-efficacy monitoring has not started or the non-efficacy boundary has not been reached, then this guideline for futility also requires that the estimated PE for the pooled VRC01 vs. control arm is < 30% and the estimated PE for the VRC01 30 mg/kg vs. control arm is < 30%.

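### The protocol and SAP set different futility targets (29 vs 21 infections), the 2.0% PrEP-scenario incidence does not follow from its stated input, and several smaller planning figures contradict their own tables; N = 2700 is unaffected

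*Protocol*

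**What the plan says.** **Futility.** Protocol 4.9.3 monitors infection counts for 90% and 65% power at PE = 60%: "The target numbers in (1) and (2) are 56 and 29, respectively". SAP 9.4 uses 90% and 50%: "The target numbers in 1. and 2. are 57 and 21, respectively". The early-completion guideline applies under the protocol when "the estimated probability of reaching 29 total infections is less than 25" percent, and under the SAP when "the estimated probability of reaching at least 21 total infections is less than 25" percent. On reporting, the protocol says "a treatment-blinded report will be generated for distribution to the OC after each DSMB meeting takes place"; the SAP says "a treatment-blinded report will be generated for distribution to the Leadership Group before each DSMB meeting takes place".

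**PrEP scenarios.** Protocol 4.6.3 states that scenarios A, B and C each give a control incidence of 2.0% per year, from 3% per year off PrEP and 90% PrEP efficacy. Section 4.6.6 uses a US off-PrEP rate of 2.1% and a South American rate of 5%.

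**Smaller items.**
- Section 4.7 claims about 87% power for 30% vs 80% and 40% vs 85%, "but may miss moderate differences (e.g., 34% power to discriminate 30% vs. 60% PE"). Table 4-4 gives 91.5%, 90.8% and 39.5%.
- Table 4-5, in the block with 18/900 controls, prints 16, 32, 80 and 160 out of 900 as 2%, 4%, 10% and 20%.
- Section 4.6.2 says about 2300 participants give 90% power, and that N = 2700 keeps 90% power down to 2.3% incidence.
- Section 4.8 gives an interval of 3.5% to 8.7% for a 6-point difference with the combined groups. Table 4-5 gives 4.05% to 7.87%.
- The Figure 4-6 caption has 1800 vs 900. Section 4.8 defines the comparison as 900 vs 900.

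**The concern.** The futility items are operative rules. The same interim data could meet the guideline in one document and miss it in the other, and the blinded projections have two recipients and two release times relative to the DSMB meeting. The SAP looks later: it places 80 weeks after last enrollment at April 17, 2020, so last enrollment was about October 5, 2018, while the protocol is dated June 15, 2017. Neither document says which one governs.

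The PrEP item sits under the claim that power remains adequate with substantial PrEP use. A reader who uses the stated 3% cannot reach 2.0%, and scenario C then falls below the 1.65% case that the text presents as the lower one.

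The other items are figures that a reader would quote from the prose and get wrong.

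**Working it through.** **Plan's own figures first.** Expected events per group are n·r·(1 − exp(−(r + d)τ))/(r + d), with d = 0.10 and τ = 80/52 years.
- Control: n = 900, r = 0.03 gives 37.6. Pooled mAb at PE = 60%: n = 1800, r = 0.012 gives 30.5. Table 4-3 has 37 and 30.
- Wald power is Φ(0.916/√(1/37.6 + 1/30.5) − 1.96) = 96.4%. Table 4-1 has 96.0%; its entries for PE 10% to 70% all reproduce within 2 points.

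**Futility targets.** Schoenfeld: events = (1.96 + z_power)² / [(1/3)(2/3)(ln 0.4)²], with denominator 0.1866.

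| Power | Events | Document |
|---|---|---|
| 90% | 56.32 | 56 (protocol), 57 (SAP): rounding only |
| 65% | 29.48 | 29 (protocol); power at 29 is 64.3% |
| 50% | 20.59 | 21 (SAP); power at 21 is 50.8% |

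Each number fits its own power floor, so the conflict is over the criterion.

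To see when each guideline would be met, take the SAP 9.4.2 model with p* = 0.03 (the PE = 0% prior). Then T* = 2700 × (1 − exp(−0.13 × 80/52))/0.13 = 3,765 person-years. The same formula returns the SAP's 2643.42 for the sister trial. With a gamma prior, the remaining infections are negative binomial. The largest count at which P(reaching the target) is still below 25%, for prior weights 1/2, 1/3 and 1/4, is:

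| Person-time accrued | Target 29 | Target 21 |
|---|---|---|
| 50% | none, 3, 6 | none, none, 1 |
| 75% | 12, 15, 16 | 5, 9, 10 |
| 90% | 21, 22, 23 | 14, 15, 16 |

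So 11 or 12 infections at 75% of person-time, or 17 to 21 at 90%, meet the probability criterion with target 29 under every weight and with target 21 under none. The highest pooled rate in the table is 23/(0.9 × 3,765) = 0.68% per year. At 1.65% control incidence and PE = 60% the pooled rate is 0.99%, and about 28 infections are expected by 75% of person-time.

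**PrEP scenarios.** Incidence = Σ (regional share) × (off-PrEP rate) × (1 − 0.9 × PrEP share).

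| Scenario | Stated 3% rate | 2.1% and 5% rates |
|---|---|---|
| A | 3 × (0.69 × 0.55 + 0.31 × 0.775) = 1.86% | 2.00% |
| B | 3 × (0.61 × 0.46 + 0.39 × 0.73) = 1.70% | 2.01% |
| C | 3 × (0.48 × 0.325 + 0.52 × 0.64) = 1.47% | 1.99% |

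The mix in 4.6.6 points the same way. Taking 5% as off-PrEP, 0.44 × 5 × 0.955 + 0.56 × 2.1 × 0.757 = 2.99%. Taking it as already net of PrEP, 0.44 × 5 + 0.56 × 1.6 = 3.10%.

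Closed-form power for PE = 60% is about 87% at 2.0%, and 84%, 81% and 75% at 1.86%, 1.70% and 1.47%. Simulation with sequential monitoring gives 83.3%, 79.4% and 74.2% for the last three. At 1.65% the figures are 79.9% (closed form), 80.4% (simulated) and 78% (protocol).

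**Dose comparison (4.7).** Simulation at 900 per arm gives 38.9%, 91.4% and 91.1% for 30/60, 30/80 and 40/85. This supports Table 4-4 and contradicts the prose.

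**Table 4-5.** 80/900 is 8.9% and 160/900 is 17.8%. The row printed as 16/900 vs 18/900 has a symmetric interval (±0.0136), as equal counts would give. The row printed as 32/900 vs 18/900 mirrors the later 18/900 vs 36/900 row. A recomputed interval for 90/900 vs 18/900 is 5.92% to 10.28% (printed 5.92% to 10.30%); 80/900 gives 4.89% to 9.08%.

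**N = 2300.** Information scales with N × incidence, so a 2.3% floor at N = 2700 implies 2700 × 2.3/3 = 2070 at 3%. Conversely, 2300 would imply a floor of 3 × 2300/2700 = 2.56%. Simulated power is 92.8% at N = 2301, 90.4% at N = 2070, and 90.5% at N = 2700 with 2.3% incidence (4,000 trials each; Monte Carlo SE 0.3 to 0.7 points across the cases simulated).

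**Safety interval (4.8).** A score interval for 180/1800 vs 36/900 is 4.05% to 7.86%, which agrees with the table.

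**Figure 4-6.** Exact Fisher power with 4% in controls is 79.8% at 7.1% and 89.3% at 7.6% for 900 vs 900, matching the quoted 80% and 90%. For 1800 vs 900 it is 90.7% and 96.4%.

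**The case against.** The best case against is that little depends on any of this.

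- **Futility.** Neither 29 nor 21 is miscalculated. SAP section 6 sends the DSMB futility report to SAP 9.4, and protocol 2.4.5 and 4.9.1 defer monitoring detail to a separate plan, so in practice the DSMB may have worked from 21. The guideline is advisory. It also requires both PE estimates (pooled, and 30 mg/kg) below 30%, and that condition always applies: the guideline can be met only below its own target, whereas "non-efficacy monitoring is commenced at at least 45 but no more than 67 pooled primary efficacy endpoints". This stands as a limit on the practical effect. It does not settle precedence, because SAP section 6 only cross-refers to the SAP's own text.
- **PrEP.** The 2.0% is recoverable and the protocol states no power at 2.0%. Its 78% at 1.65% already covers recomputed A and B; only C falls below. All of this stands. The 2.1% and 5% reading is a good inference but still an inference: 4.6.6 words the 5% ambiguously, and both 2.99% and 3.10% round to 3%.
- **N = 2300.** Figure 4-1 is not shown, and the 56-event target against 67 expected events gives 2700 × 56/67 = 2,257, close to 2300. But that is the Schoenfeld route, and 4.6.2 names the Wald test for both of its figures, so the tension within that paragraph remains. The simulation used here is not seqDesign and runs 2.4 points above the protocol's 78% at 1.65%, so the replacement number should come from the sponsor's own re-run.
- **Rest.** These are editorial, and they are treated as such.

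**Conclusion.** The concern holds. Severity rests on two items.

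1. The futility target and reporting route exist in two versions: 29 vs 21 infections, or 64% vs 51% power. The gap decides whether the probability criterion is met at 11 to 12 infections (75% of person-time) or 17 to 21 (90%), whichever of the three prior weights is used. This assumes the SAP 9.4.2 model and the PE = 0% prior. Counts that low need a pooled incidence below about 0.7% per year.
2. The PrEP scenarios state an input that gives 1.86%, 1.70% and 1.47% instead of 2.0%. If 3% was really meant, power for PE = 60% is about 84%, 81% and 75%. If 2.1% and 5% were meant, 2.0% stands and only the stated input is wrong.

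The remaining items are minor. The 4.7 prose understates power by about 4 to 5.5 points, about 2300 overstates the N needed, and the 4.8 interval is too wide (5.2 vs 3.8 points); all three err conservatively. Four Table 4-5 numerators and one figure caption are wrong. An earlier design with 800 per arm would explain the numerators, but no document says so. N = 2700 and Table 4-1 are unaffected.

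**What to change.** - **Futility:** the sponsor, oversight body and DSMB should reconcile protocol 4.9.3 and SAP 9.4 on one target, one recipient and one time for the blinded report, and state which document governs. Cost: one decision and a short clarification.
- **PrEP scenarios (4.6.3):** either replace the 3% off-PrEP input with the regional rates of 2.1% and 5%, or keep 3% and restate the incidences as 1.86%, 1.70% and 1.47% with their powers.
- **Section 4.7:** quote 39.5%, 91.5% and 90.8% from Table 4-4.
- **Table 4-5:** change the four numerators to 18, 36, 90 and 180.
- **Section 4.6.2:** re-run seqDesign and restate the N for 90% power so that it agrees with the 2.3% floor.
- **Section 4.8:** quote 4.05% to 7.87%.
- **Figure 4-6 caption:** change 1800 to 900.

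Apart from the futility decision, the cost is text edits and one simulation re-run. Sample size and analysis do not change.
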